11.3 Secondary Objectives

An important hypothesis underlying the rationale for the combination therapy is that initial progression on PD-1 blockade alone results from poor T cell recruitment. Consequently, our first secondary endpoint will evaluate this by comparing the quantitative CD8+ expression levels between patients who eventually respond and patients who do not respond using a two-sample t-test and control the type I error at the two-sided 0.05 level. Assuming that the trial accrues to completion, 90% compliance in tissue and biopsy

submission, there will be 56 patients to evaluate this hypothesis. If it is further assumed that 25% of these patients respond, then we anticipate 80% power to detect a mean difference in CD8+ expression of 0.875 standard deviations. Evaluation of this hypothesis motivates the unbalanced randomization.

For the additional secondary objectives, the study will estimate the response rate (confirmed and unconfirmed, complete and partial responses) in each arm and construct 95% binomial confidence intervals. All randomized patients will be included in the analysis of response. Patients who cannot have their exact response determined due to inadequate disease assessments will be counted in the denominator as non-responders.

We will also construct Kaplan-Meier plots and estimate the median Overall Survival (OS) and construct 95% Brookmeyer-Crowley Confidence intervals. We will be able to estimate the ORR or the OS rates at a particular time point (e.g. 13 weeks) to within 12.3% (95% confidence interval (CI)) and 21.4% in the combination therapy and ipilimumab alone arms, respectively. Waterfall plots will be constructed to represent each patient's best change in tumor burden.

Toxicity will be assessed in each arm separately. Any toxicity with at least 5% chance of occurring has 93.7% and 60.3% chance of being observed at least once in the combination therapy and ipilimumab alone arms, respectively. We will be able to estimate the rate of occurrence of any particular toxicity to within 12.3% (95% CI) and 21.4% in the combination therapy and ipilimumab alone arms, respectively.

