1.2 Secondary Objective(s)

- a. To estimate difference in T-cell infiltrate between on-study biopsy samples of patients who respond to combination therapy (including confirmed and unconfirmed, complete and partial response per RECIST 1.1, in each treatment arm).
- b. To evaluate the objective response rate (ORR), defined as confirmed complete or partial response per RECIST 1.1, in each treatment arm.
- c. To evaluate the overall survival (OS) of patients in each treatment arm.
- d. To evaluate the toxicity profile of patients in each treatment arm.

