- A To be performed on or prior to Day 1 and on Day 21-35 (Day 28 +/- 7 days). The first biopsy should be performed within 28 days prior to Day 1. If it is not feasible to obtain this biopsy, tissue that was collected at any time since demonstrated progression on PD-1 or PD-L1 therapy may be substituted provided that 30 unstained slides are available.
- B Only for patients with symptoms of congestive heart failure (CHF), cardiomyopathy, myocarditis, myocardial infarction, or exposure to cardiotoxic medications. Required pre-registration (see [Section 5.3n](#)). After that, perform as clinically indicated.
- C Free T3 and Free T4 are only required if TSH results are abnormal.
- D Only for patients with a known history of congestive heart failure (CHF), cardiomyopathy, myocarditis, myocardial infarction, exposure to cardiotoxic medications, or with a clinical history suggestive of any of these conditions. Required pre-registration (see [Section 5.3m](#)). After that, perform as clinically indicated.
- E Collected prior to previous anti-PD-1 or anti-PD-L1 treatment
- F To be drawn on or prior to Day 1 (after registration and within 28 days) and on Day 21-35 (Day 28 +/- 7 days). If feasible, Day 1 blood should be drawn on the same day as the baseline tissue biopsy. Day 28 Blood must be drawn on same day as the Day 28 tissue biopsy.
- G Required time frame is detailed in [Section 5.0](#).
- H Only for females of reproductive potential (see [Section 5.3p](#))
- J Only required for patients with a known history of HIV (see [Section 5.3g](#))
- K Weeks measured from start of treatment, provided that the patient does not have any treatment delays
- L If pre-registration exam/lab was performed within 14 days prior to Cycle 1 Day 1, this exam/lab does not need to be repeated on Cycle 1 Day 1.
- M Performed at completion of Week 12
- N Every 12 weeks until progression
- P Every 3 weeks until resolution of adverse events
- Q At least every 6 months (+/- 2 weeks) until 2 years after registration, then annually (+/- 4 weeks) until 3 years after registration.
- R Though weight should be checked at each visit, weight-based dosing should be calculated using baseline weight unless weight has changed from last dose by more than 10%.

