10.3 Best Response

This is calculated from the sequence of objective statuses.

- a. CR: Two or more objective statuses of CR a minimum of four weeks apart documented before progression or symptomatic deterioration.

- b. PR: Two or more objective statuses of PR or better a minimum of four weeks apart documented before progression or symptomatic deterioration, but not qualifying as CR.
- c. Unconfirmed CR: One objective status of CR documented before progression or symptomatic deterioration but not qualifying as CR or PR.
- d. Unconfirmed PR: One objective status of PR documented before progression or symptomatic deterioration but not qualifying as CR, PR or unconfirmed CR.
- e. Stable/no response: At least one objective status of stable/no response documented at least 6 weeks after registration and before progression or symptomatic deterioration, but not qualifying as anything else above.
- f. Increasing disease: Objective status of progression within 12 weeks of registration, not qualifying as anything else above.
- g. Symptomatic deterioration: Objective status of symptomatic deterioration within 12 weeks of registration, not qualifying as anything else above.

Inadequate assessment, response unknown: Progression or symptomatic deterioration greater than 12 weeks after registration and no other response category applies.

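### Objective 1.2b defines ORR as confirmed response, but Section 11.3, the only by-arm response-rate analysis, counts unconfirmed responses as well

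*Combined protocol and SAP*

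**What the plan says.** The second secondary objective, Section 1.2b, reads: "To evaluate the objective response rate (ORR), defined as confirmed complete or partial response per RECIST 1.1, in each treatment arm".

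Section 11.3, in the paragraph on the additional secondary objectives, states that "the study will estimate the response rate (confirmed and unconfirmed, complete and partial responses) in each arm and construct 95% binomial confidence intervals". On the denominator it adds: "All randomized patients will be included in the analysis of response". The next paragraph gives the precision: "We will be able to estimate the ORR or the OS rates at a particular time point (e.g. 13 weeks) to within 12.3" percent in the combination arm, and 21.4 percent in the ipilimumab arm. Section 11.3 defines no other response rate, and no other section plans one by arm. The by-arm work in Appendix 18.1 consists of classification and association analyses of biomarkers.

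Section 10.3 treats the two kinds of response as separate categories. A confirmed PR needs "Two or more objective statuses of PR or better a minimum of four weeks apart documented before progression or symptomatic deterioration". One status is enough for the other category: "Unconfirmed PR: One objective status of PR documented before progression or symptomatic deterioration but not qualifying as CR, PR or unconfirmed CR". CR is split in the same way.

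The wider definition also appears in Sections 1.2a and 11.1, where it identifies responders for the T-cell comparison.

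**The concern.** The two sections count different patients under one name. A statistician who programs 11.3 as written will report a rate that includes responses seen once and never confirmed. A reader who goes to 1.2b will take that rate as confirmed. Since the documents do not settle which is the headline, the choice could also be made after the data are seen.

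The scan schedule makes the difference a practical one. Confirmation takes a second qualifying assessment at least four weeks after the first, but the calendar offers one only every 12 weeks. A response that is lost between two scheduled scans is counted under one definition and not under the other.

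The level of the ORR also carries weight in the argument of the protocol. Section 2.0 says that a clear improvement on a 10% background response rate with ipilimumab alone would be important preliminary data. It does not say whether that 10% is confirmed, so a reader needs to know which rate is being set against it.

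**Working it through.** **1. The plan's own precision figures.** The 95% half-width at p = 0.5 is 1.96 × √(0.25/n).

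- n = 63 (combination arm, Section 11.1): 1.96 × √(0.25/63) = 12.35%, stated as 12.3%.
- n = 21 (ipilimumab arm): 1.96 × √(0.25/21) = 21.38%, stated as 21.4%.

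Both reproduce. They depend only on n and p = 0.5, so they fit either definition and do not show which was meant.

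**2. When a response can be confirmed.** The first post-baseline scan is "Performed at completion of Week 12" in both arms (Sections 9.1 and 9.2, footnote M). After that, Arm 1 is scanned "Every 12 weeks until progression" (9.1, footnote N), and Arm 2 at the end of Weeks 24, 36 and so on (9.3, footnote M). Without an extra scan, a response first seen at Week 12 can be confirmed at Week 24 at the earliest. With progression by Week 24:

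| Status at Week 12 | By Week 24 | Section 11.3 | Section 1.2b |
|---|---|---|---|
| PR | progression | responder | non-responder |
| PR | PR or better | responder | responder |

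The 13 weeks given as an example in the precision sentence may refer to OS alone. If it also refers to ORR, only one scheduled post-baseline scan has been done by then, and no response could have been confirmed by a scheduled scan.

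**3. Shift per unconfirmed response.**

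- Planned arm sizes: 1/63 = 1.6 points; 1/21 = 4.8 points.
- All randomized patients: Section 11.1 gives 94 in total after allowing for 10% ineligibility. Applying the 3:1 ratio gives 94 × 3/4 = 70.5 and 94 × 1/4 = 23.5, about 70 and 24. Then 1/70 = 1.4 points and 1/24 = 4.2 points.

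**4. Illustration for the combination arm.** The documents give no unconfirmed share, so shares of 20% and 40% are assumed. The 25% planning rate of Section 11.1 is taken as confirmed plus unconfirmed, which is how that section defines a responder. Responders: 0.25 × 63 = 15.75, rounded to 16; 0.25 × 70 = 17.5, rounded to 18. Confirmed counts are 16 × 0.8 = 12.8 (13), 16 × 0.6 = 9.6 (10), 18 × 0.8 = 14.4 (14) and 18 × 0.6 = 10.8 (11). Intervals are exact (Clopper-Pearson) 95%.

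| Assumed unconfirmed share | n = 63 | n = 70 |
|---|---|---|
| none | 16/63 = 25.4% (15.3–37.9) | 18/70 = 25.7% (16.0–37.6) |
| 20% | 13/63 = 20.6% (11.5–32.7) | 14/70 = 20.0% (11.4–31.3) |
| 40% | 10/63 = 15.9% (7.9–27.3) | 11/70 = 15.7% (8.1–26.4) |

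**5. Against the 10% background rate.** With n = 63, 12 confirmed responses give 19.0% (10.2–30.9) and 11 give 17.5% (9.1–29.1). The lower limit therefore drops below 10% once 5 of the 16 responses are unconfirmed. With n = 70, 13 give 18.6% (10.3–29.7) and 12 give 17.1% (9.2–28.0), so the change comes at 6 of 18. The plan sets no rule that compares a confidence limit with 10%; this only shows how the reading could change.

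**The case against.** The strongest reply is that 1.2b may be the slip, not 11.3. The wider definition appears three times (1.2a, 11.1 and 11.3) and the confirmed one only once. In 11.3 the wider definition is attached to the response rate, and the term ORR comes one paragraph later in a sentence about precision, so the text never states outright that they are the same quantity. Both observations are accurate. They bear on which section to amend, and for that reason the choice is left to the sponsor. They do not remove the conflict. If ORR in the precision sentence does mean the confirmed endpoint of 1.2b, the plan gives a precision for that endpoint but no analysis that estimates it.

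The second reply is that little depends on it. ORR is estimated without a test or decision rule, and Section 10.3 already separates the categories, so either rate can be produced from the planned data. The shifts illustrated above (at most 25.7 − 15.7 = 10.0 points) lie within the stated 12.3-point half-width. This stands, and it limits the weight of the point. It does not make the planned analysis match the stated endpoint.

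The comparison with 10% and the unconfirmed shares are not taken from the plan. They are illustration, and the conclusion does not rest on them.

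**Conclusion.** The concern holds. As written, Section 11.3 does not estimate the endpoint defined in Section 1.2b. This follows from the text alone and needs no assumption. On the planned arm sizes, each unconfirmed response shifts the reported rate by 1.6 points in the combination arm and 4.8 points in the ipilimumab arm. The total difference is unknown. The 20% and 40% cases, which would lower a combined rate of about 25% to about 20% or 16%, rest on assumed shares. This should be corrected, but it does not threaten the main conclusion of the trial: the PFS comparison and the futility rule do not use ORR.

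**What to change.** Before response data are analysed, make Sections 1.2b and 11.3 use one definition of ORR. There are two ways:

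- Section 11.3 estimates confirmed ORR by arm as 1.2b defines it, and reports confirmed plus unconfirmed response as a labelled supportive estimate; or
- Section 1.2b is amended, if the wider definition was intended.

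The wider responder definition for the T-cell comparison in 1.2a and 11.1 can stay. Section 11.3 should also say whether the 13-week example applies to ORR or only to OS.

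The cost is a change of wording. No new data are needed. Keeping the confirmed definition may give a lower headline ORR; widening 1.2b means that the ORR will include responses that were never confirmed.

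A minor matter can be settled in the same edit. The 12-week cut-off in 10.3f and 10.3g runs from registration, while the first scan is timed from treatment start, which Section 13.1 allows to be up to seven days later. Depending on the scan window, progression at an on-time first scan could be labelled as response unknown. The cut-off should cover the first scheduled assessment. This affects best-response labels only, not the ORR.

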11.0 STATISTICAL CONSIDERATIONS

11.1 Accrual Goal

Although the primary objective aims to assess whether combination therapy ipilimumab and nivolumab is superior to single therapy ipilimumab in patients who have previously progressed on anti-PD-1 or anti-PD-L1 therapy, major additional objectives of this study include assessment of key biomarkers and genomic correlatives, particularly for patients who receive combination therapy. This study will use a design in which 63 patients will be randomized to receive combination therapy ipilimumab and nivolumab and 21 patients will be randomized to receive single therapy ipilimumab. Assuming an ineligibility rate of 10% the total accrual goal is 94 patients.

The unbalanced randomization is motivated by the necessity of evaluating the first secondary objective. In particular, the underlying rationale for the combination therapy is that initial progression on PD-1 blockade alone results from poor T cell recruitment. If the combination therapy is superior to single agent ipilimumab, evaluation of this hypothesis by comparing T cell infiltration between patients who have an objective response (confirmed and unconfirmed partial or complete response per RECIST 1.1) and patients who do not have an objective response to combination therapy will elucidate mechanisms that are imperative for design and development of further studies of combination therapy in this population. Thus, unbalanced randomization is necessary to ensure adequate sample size for evaluating this hypothesis. Assuming a response rate of 25% and 90% compliance in tissue and biopsy submission, then we anticipate accruing 14 eligible objective responders and 43 eligible objective non-responders in the combination therapy arm.

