Although our primary analysis will focus on developing classification models, we will also assess the association between response and each individual marker, clonality, mutational load, mRNA expression signature, and ctDNA fraction. The analysis will be again conducted separately by treatment arm. For each of the IHC markers, clonality, and ctDNA fraction, we will test for difference in mean levels between responders and non-responders using two-sample t-tests. We assume we obtain data on 90% of patients and that the response rates are 15% and 30% in arms 1 and 2, respectively. Then at the nominal $\alpha=0.05$ level, we anticipate 80% power to detect a difference in marker level, clonality, or ctDNA fraction between responders and non-responders of 1.9 and 0.83 standard deviations in Arms 1 and 2, respectively. Further, we will also assess whether individual mRNA transcripts and genes are associated with response. Specifically, we will compare the expression between patients who respond and who do not respond using two-sample t-tests again. We will accommodate multiple testing by controlling the false discovery rate. With the same response rate and sample size assumptions as before, and further assuming that 80% of genes are not associated with response, then at the FDR = 5% level, we anticipate 80% power to detect a difference in expression level of 2.43 and 1.33 standard deviations in Arms 1 and 2, respectively. Note that t-tests are used since they can be more powerful than logistic regression, but for all association analyses in this objective and subsequent translational medicine objectives, we will consider the use of alternative approaches, e.g. data transformation, Wilcoxon tests or logistic regression, if there are outliers or influential points.

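### Two planning figures do not follow from the plan's own inputs: the toxicity-detection probabilities (Section 11.3) and the Arm 2 mRNA detectable difference (Section 18.1c)

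*Combined protocol and SAP*

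**What the plan says.** Section 11.1 sets the arm sizes: "63 patients will be randomized to receive combination therapy ipilimumab and nivolumab and 21 patients will be randomized to receive single therapy ipilimumab". The 10% ineligibility allowance is added on top of these to reach the accrual goal of 94 (84/0.9 = 93.3), so 63 and 21 are already net of it.

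Section 11.3 makes two consecutive statements about toxicity. The first is "Any toxicity with at least 5% chance of occurring has 93.7% and 60.3% chance of being observed at least once", in the order combination arm, ipilimumab arm. The second is "We will be able to estimate the rate of occurrence of any particular toxicity to within 12.3% (95% CI) and 21.4" per cent, in the same order. An earlier sentence in the section gives the same precision for response and survival: "We will be able to estimate the ORR or the OS rates at a particular time point (e.g. 13 weeks) to within 12.3" per cent in the combination arm, and 21.4% in the ipilimumab arm.

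The Objective 1 paragraph of the Statistical Plan in Section 18.1 sets the inputs for comparing responders with non-responders: "We assume we obtain data on 90% of patients and that the response rates are 15% and 30% in arms 1 and 2". At a nominal alpha of 0.05 it gives 80% power for differences "between responders and non-responders of 1.9 and 0.83 standard deviations in Arms 1 and 2, respectively". For mRNA transcripts it carries over the same response rates and sample sizes, "further assuming that 80% of genes are not associated with response, then at the FDR = 5% level", and concludes "we anticipate 80% power to detect a difference in expression level of 2.43 and 1.33 standard deviations in Arms 1 and 2, respectively".

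**The concern.** The two toxicity sentences describe the same endpoint in the same patients, but their figures imply different sample sizes, and the section names no separate toxicity denominator. In the mRNA paragraph, moving from alpha 0.05 to the FDR criterion raises the Arm 1 figure from 1.9 to 2.43 SD (a factor of 1.28) and the Arm 2 figure from 0.83 to 1.33 SD (a factor of 1.60). The smaller arm has fewer degrees of freedom and should pay the larger penalty for a stricter alpha, so the larger factor in Arm 2 is suspect.

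What is at stake is whether a reader can reproduce the plan's statements of what the trial can detect. Section 11.1 counts biomarker and genomic assessment among the study's major additional objectives, so these figures may be relied on when the translational results are judged.

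**Working it through.** **Toxicity detection**

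Inputs: n = 63 and 21 (Section 11.1); true rate 5% (Section 11.3). The chance of seeing at least one event is 1 − 0.95^n. The 95% half-width at its widest is 1.96 × √(0.25/n).

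| n | Chance of at least one event | Half-width |
|---|---|---|
| 63 | 96.05% | 12.35% |
| 21 | 65.94% | 21.39% |
| 54 | 93.73% | 13.34% |
| 18 | 60.28% | 23.10% |

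The printed precision (12.3% and 21.4%) is reproduced by 63 and 21. The printed detection probabilities (93.7% and 60.3%) are reproduced by 54 and 18. Solving for n from the rounded values gives 53.74 to 54.05 and 17.99 to 18.04, so no other whole numbers fit. Against the printed figures, the gaps at 63 and 21 are 96.05 − 93.7 = 2.35 points and 65.94 − 60.3 = 5.64 points.

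**mRNA detectable difference**

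Inputs from Section 18.1c: data on 90% of patients, response of 15% (Arm 1) and 30% (Arm 2), two-sample t-test, 80% power, FDR 5%, 80% of genes null. The test is taken as two-sided. Expected group sizes, responders versus non-responders:

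- Arm 1: 0.9 × 21 = 18.9, giving 2.835 v 16.065.
- Arm 2: 0.9 × 63 = 56.7, giving 17.01 v 39.69.

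The plan does not say how FDR is turned into a per-gene alpha. I use the usual conversion, FDR × (non-null share) × power / [(null share) × (1 − FDR)] = 0.05 × 0.2 × 0.8 / (0.8 × 0.95) = 0.0105.

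Detectable differences at 80% power from the noncentral t distribution:

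| Quantity | Recomputed (SD) | Printed (SD) |
|---|---|---|
| Arm 1, alpha 0.05 | 1.916 | 1.9 |
| Arm 2, alpha 0.05 | 0.827 | 0.83 |
| Arm 1, FDR | 2.429 | 2.43 |
| Arm 2, FDR | **1.016** | **1.33** |

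The same method also reproduces the 0.875 SD for CD8+ expression in Section 11.3 (14.175 v 42.525, alpha 0.05: 0.8747). Only the 1.33 fails.

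Sensitivity of the Arm 2 result:

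- Whole patients: 17 v 40 gives 1.015, 17 v 39 gives 1.019, and 16 v 38 gives 1.046.
- Per-gene alpha of 0.0100 gives 1.022; 0.0125 gives 0.996.
- To reach 1.33 SD on the stated Arm 2 groups, the per-gene alpha would have to be about 0.00048. At that alpha Arm 1 would be 3.41 SD, not 2.43.
- Power at 1.33 SD on the stated inputs is 0.971.

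**The case against.** There are four points on the other side.

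- **Nothing depends on these figures.** No stopping rule, sample size or primary power uses them, and both err on the safe side. The toxicity figures even remain true as lower bounds at 63 and 21. This stands, and it limits the point to a minor correction. It does not make the figures right as stated.
- **A reduced toxicity population may have been meant.** The counts 54 and 18 do appear in Section 18.1c, but only for exome data. The plan applies its 90% factor to tissue and data availability, never to toxicity, and 90% of 63 and 21 (56.7 and 18.9) would give 94.5% and 62.1%, not the printed values. If 54 and 18 were intended, the precision sentence is the wrong one. Either way the two sentences disagree.
- **The FDR conversion is assumed.** This is fair. In addition, the exact match to 2.43 SD uses fractional expected group sizes; whole patients give 2.37 (3 v 16) or 2.40 (3 v 15). Neither point brings Arm 2 near 1.33, and no single per-gene alpha fits both arms.
- **mRNA tissue comes from selected sites only,** so the real number may be smaller and 1.02 SD optimistic. That may be so in practice, but the paragraph expressly keeps the earlier sample sizes, and the Arm 1 figure agrees with them. With fewer patients, 2.43 SD in Arm 1 would need recomputing too.

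**Conclusion.** Both discrepancies are real. On the design's 63 and 21 patients, the toxicity-detection probabilities should read 96.1% and 65.9%; the printed 93.7% and 60.3% are about 2.4 and 5.6 points too low. This part needs only the stated sample sizes and the 5% rate.

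The Arm 2 mRNA detectable difference is about 1.02 SD on the stated inputs (1.01 to 1.05 with whole-patient groups), against the printed 1.33. This part rests on a two-sided t-test and the usual FDR conversion, both supported by agreement with the plan's other figures. The source of 1.33 cannot be determined from the documents. More than one set of inputs gives roughly that value: 15% response with 54 or 55 patients gives 1.338 or 1.325, and 30% response with 34 to 35 patients gives about 1.33.

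The effect is confined to stated secondary-safety and translational planning properties. Sample size, primary power, analysis and conduct are unaffected.

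**What to change.** 1. **Section 11.3.** Use one toxicity denominator in both sentences. Replacing 93.7% and 60.3% with 96.1% and 65.9% matches the 63 and 21 used in the precision sentence. If 54 and 18 evaluable patients were intended, state that and its reason, and change the toxicity precision to 13.3% and 23.1%.
2. **Section 18.1c, Objective 1.** Restate 1.33 SD as about 1.02 SD and give the FDR-to-alpha conversion used. If fewer patients are expected to supply mRNA tissue, replace the carried-over sample size with the expected number per arm and recompute both arms.

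The cost is two text corrections.
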